**COMPLIANCE STATEMENT**

This Study will be conducted in accordance with this Protocol, the Declaration of Helsinki, applicable Good Clinical Practices and applicable regulations and standards (e.g., US 21 CFR Parts 50, 56, 812, and 820.30, US 45 CFR Part 46, ISO 14155:2020, and ISO 13485) and the appropriate local legislation(s).

The most stringent requirements, guidelines or regulations must always be followed. The conduct of the study will be approved by the appropriate Review Board (IRB) of the respective sponsor locations and by the applicable regulatory authorities, when applicable.

## PROTOCOL SUMMARY

Protocol Number	IRT-003-2024
Title	Design Validation Study: Extended Wear Performance of the Zio monitor 
Objective	
To evaluate the wear performance of the Zio monitor device in a representative population over an extended wear period (of up to 30 continuous days) to demonstrate that the device can be worn with adequate patch adherence and signal quality through 21 days.
 
Assessment of wear performance will include evaluation of the wear duration of the patch and percentage of analyzable electrocardiographic time.
 
Product safety will be assessed by collection of all adverse events.

Study Device	Zio monitor
Targeted Number of Participants	
A total of up to 75 participants will be enrolled at US locations. The study may enroll participants from the community surrounding San Francisco, CA and Deerfield, IL as referred by FieldWork® (or another recruitment vendor) at the iRhythm clinic in those locations.
 
The study may also enroll participants from identified clinical locations at up to 3 additional health care institutions.

Study Design	A Prospective, multi-center, single-arm study to validate the design of the Zio monitor/Zio MCT device form factor in extended (21-day) wear.
Performance Objectives and Measures	
Performance Objectives
 
Mean wear duration and percent analyzable time of the Zio monitor will be assessed. Performance goals include mean wear duration of 21 days and percent analyzable time of 80%.
 
Performance objectives will be met if the mean wear duration is greater than 21 days, and percent analyzable time is greater than 80% in 90% of subjects.
 
Safety Measures

	
The proportion of participants that experience clinically significant skin irritation through 30 days of wear will be assessed through capture and reporting of all adverse events.
 
Additional Device Measures
 
 
• Signal Artifact (%) – Defined as the proportion of ECG signal that is artifact over the wear duration, reported for each study device.
 
• Device Functionality (%) – Defined as the proportion of Zio monitors recording a continuous ECG signal through 21 days, and through 30 days.
 
 
Other Measures
 
Observational assessment of participant skin types that will be reported include:
 
 
• Participant Skin Type – Dry, Oily, Normal (Baseline only)
 
• Known Hyperhidrosis Status – Primary, Secondary or None (Baseline only)
 
• Fitzpatrick Skin Type (Baseline only)
 
• Chest Hair Density – e.g., smooth/no hair, some hair, moderately hairy, or very hairy (baseline and follow-up) in the target patch placement area
 

Participant Visits	
On-location visits are planned for Baseline (time of patch application), 21 days, and 30 days following patch application.
 
Telephone calls to the participants are planned for 7-day and 14-day visits.

Inclusion Criteria	
 
1. Participant must be 18 years or older at time of informed consent.
 
2. Participant is willing and able to provide informed consent and be able to complete all visits for the study.
 

Exclusion Criteria	
 
1. Participant has a known allergy to adhesives.
 
2. Participant has a current skin infection or injury at location for study device placement.
 
3. Participant is a member of a vulnerable population.
 
4. Participant is a current or prior employee of iRhythm.
 
5. Participant is unable or unwilling to participate or comply with study protocol.
 
6. The local Investigator deems the participant has a condition that could limit the participant's ability or willingness to participate in the study, or ability to comply with study required procedures and/or follow-up visits.
 
7. Participant has experienced symptomatic episodes where instance variations in cardiac performance could result in immediate danger to the participant.
 

	

8. Participant has an external cardiac defibrillator or may be exposed to high frequency surgical equipment near strong magnetic fields or devices such as MRI during the wear period.

9. Participant has a neuro-stimulator, as it may disrupt the quality of ECG data.

10. Participant does not have the competency to wear the device for the prescribed monitoring period.

11. Participant does not have the ability to consent for themselves (i.e., no LARs).

Analysis Populations	
All analyses will be performed on the population of enrolled participants on whom the Zio monitor application was attempted. The age, sex at birth, and application type (HCP designee vs. self-application) of participants will be monitored throughout the enrollment period to ensure representation across key user groups.
 
Performance within subgroups including (but not limited to) sex at birth, age, and application type will be assessed.

 The study device includes the wearable ECG adhesive assembly and symptom button common to both the Zio monitor and next generation Zio AT (Zio MCT) ambulatory cardiac monitoring devices. The gateway associated with Zio MCT necessary for transmission of ECG data during device wear will not be included as part of this study. For simplicity, the study device will be referred to Zio monitor within this protocol. Additional information regarding the study device is included in Section 2.3.

## 1.0 INTRODUCTION

### 1.1 Study Design

This study is a prospective, multi-center, single-arm study to validate the design of the Zio® monitor/Zio MCT® device form factor in extended (21-day) wear.

### 1.2 Study Objectives

The objective of the study is to evaluate the wear performance of the Zio monitor device in a representative population over an extended wear period (of up to 30 continuous days) to demonstrate that the device can be worn with adequate patch adherence and signal quality through 21 days. Assessment of wear performance will include evaluation of the wear duration of the patch and percentage of analyzable electrocardiographic time. Product safety will be assessed by collection of all adverse events.

## 2.0 BACKGROUND AND RATIONALE

Patients who are suspected of suffering from an arrhythmia-related condition typically undergo electrocardiography (ECG) monitoring. Clinical symptoms associated with arrhythmia may include palpitations, shortness of breath, dizziness, lightheadedness, pre-syncope, syncope, or anxiety. Arrhythmias may also present asymptotically. Arrhythmias often occur infrequently and may not be detected with in-clinic 12-lead ECG monitoring (which records 10 seconds of data), or traditional ambulatory monitoring (i.e., with a Holter device up to 48 hours). Long-term 14-day continuous ambulatory ECG monitoring is useful for the detection of infrequent arrhythmic events [1], though further extending the monitoring period may aid in detection of additional arrhythmias and provide additional clinical insights.

The Zio monitor (K202359) received FDA 510(k) clearance on May 21, 2021 and is a long-term continuous ambulatory patch ECG monitor which adheres to the patient's left pectoral region. Additional description of the device is provided in **Table 1**. The Zio monitor is substantially equivalent to the predicate Zio XT device but is designed to be smaller and more than 50% lighter.

The Zio monitor is breathable with a waterproof housing, and a more flexible design for a secure attachment. These refinements allow for a more comfortable wear experience [2] with longer wear times and, therefore, provide more complete diagnostic data [3].

Like the predicate Zio XT device, Zio monitor is currently indicated for long-term continuous monitoring of up to 14 days. However, successful performance verification testing at iRhythm has demonstrated that the Zio monitor is capable of recording continuous ECG data for up to 21 days.

This extended wear clinical design validation study will assess the extended wear performance of the Zio monitor device, by having participants wear the device for as long as possible (up to 30 days) and recording their experience.

The study device includes the wearable ECG adhesive assembly and symptom button common to both the Zio monitor and next generation Zio AT (Zio MCT) ambulatory cardiac monitoring devices. The gateway associated with Zio MCT necessary for transmission of ECG data during device wear will not be included as part of this study. For simplicity, the study device will be referred to Zio monitor within this protocol. Additional information regarding the study device is included in Section 2.3.

The Zio monitor device should not be submerged in water. During a bath, keep the device above water. Please refer to the Zio monitor labeling instructions or Patient Guide for the full set of details.

Additionally, the percentage of analyzable ECG signal (i.e., percent analyzable time) will be assessed against a performance benchmark of 80%. The device tested in this extended wear study will be the design cleared in K202359, with minor improvements for manufacturability and with the programming configurations updated to allow for continuous ECG data recording for up to 30 days. Performance objectives include a mean wear time of at least 21 days, and percent analyzable time (i.e., artifact-free ECG signal) greater than 80% for at least 90% of study participants.

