**Table 1: Device Comparison (Substantial Equivalence Summary)**

Feature	Predicate Commercial Device: Zio® XT Patch (K121319)	Study Device: Zio® monitor (K202359)
Indications for Use		
Indications for Use Statements	The Zio® Patch is a prescription-only, single-patient-use, continuously recording ECG monitor that can be worn up to 14 days. It is indicated for use on patients who may be asymptomatic or who may suffer from transient symptoms such as palpitations, shortness of breath, dizziness, lightheadedness, presyncope, syncope, fatigue, or anxiety.	The Zio® monitor is a prescription-only, single-patient-use ECG monitor that continuously records data for up to 14 days. It is indicated for use on patients who may be asymptomatic or who may suffer from transient symptoms such as palpitations, shortness of breath, dizziness, lightheadedness, pre-syncope, syncope, fatigue or anxiety.
General Characteristics		
Classification	Class II: 21CFR870.2800	Same
Product Code	DSH	Same
Patient Environment	Ambulatory	Same
Patient Population	Non-pediatric, non-critical care patients	Same
Programmed ECG Storage Duration	14 days	Up to 30 days
Technological Characteristics		
Event Trigger	Manually by patient	Same
Size	The Zio Monitor has a reduced form factor	
Performance Characteristics		
Weight	24.7 g	10.0 g
Dimensions	5.2 x 2.0 x 0.5 in	5.5 x 2.2 x 0.4 in
Photograph or Drawing		

Feature	Predicate Commercial Device: Zio® XT Patch (K121319)	Study Device: Zio® monitor (K202359)
	 Zio XT (K121319)	 Zio® monitor (K202359)

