# 3.0 STUDY PERFORMANCE OBJECTIVES AND ADDITIONAL MEASURES

## 3.1 Wear Time Performance Objective

Wear duration is defined as the number of days the patch is attached to the participant. Wear duration measurement will start at the time of device application and will end at any of the following events:

- the device is removed at the 30-day follow-up visit, or
- the device fails to adequately adhere to the skin

All enrolled participants on whom patch application was attempted will be included as part of the mean wear duration analysis. However, participants who discontinue wear of the device for reasons outside of the study protocol, or occurrence of an adverse event not related to the study, will not be counted in the analysis. Full disclosure for reasons of discontinuation will be provided in the study report.

Mean wear duration will be compared to a performance goal of 21 days. The performance objectives will be met if the mean wear duration is greater than 21 days.

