## 3.2 Analyzable Time Performance Objective

Analyzable time is the percentage of time during the wear of the Zio monitor device which yields analyzable ECG signal (i.e., free from signal artifact).

All enrolled participants in whom patch application was attempted will be included as part of the percent analyzable time analysis. However, participants who discontinue wear of the device for reasons outside of the study protocol, or occurrence of an adverse event not related to the study, will not be counted in the analysis. Full disclosure for reasons of discontinuation will be provided in the study report.

Percent analyzable time will be compared to a performance objective of 80%. The performance objective will be met if the percent analyzable time is greater than 80% in 90% of subjects.

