**5.2 Patch Wear Period**

All consented participants in whom the Zio monitor Patch application is attempted will be considered enrolled in the study. Patch application is considered to have been attempted when the Zio monitor Patch kit is opened and the first step necessary for skin preparation has been initiated. The participant will be instructed to wear the device for as long as possible, up to the 30-day visit.

Study participants will be instructed to press and hold along the edges of the patch if they notice the patch peeling or lifting at the edges during the wear period. If a patch completely detaches from the participant's chest, the patch will not be re-applied. In the case of early patch detachment, the participant should notify study staff of the date and time of detachment, and a study completion visit should be scheduled as soon as possible.

At any time after patch application, if the device is determined to no longer be functioning (for example, if a rapidly blinking orange light is observed), the device will not be replaced. The date and time the determination of function failure will be noted as close to accurate as possible. As a non-functioning device does not present a safety concern, the participant will be asked to continue wearing the non-functioning patch for as long as possible, in order to record wear duration and wear experience data.

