### **5.6 30-Day (±3 days) Participant Follow-up (Visit 5)**

At day 30 following patch application and up to day 33, participants will be asked to return to the clinic and the following activities will be conducted:

- Skin assessment by HCP or designee, including photograph of the area with the device on and also upon device removal
- Adverse Event review
- Zio patch removal and visual inspection, including photograph of front and back of patch
- Patch return to iRhythm Technologies, Inc. for data download and evaluation

Participants who applied the Zio to themselves at the Baseline visit will be asked to remove the patch. They may ask a Study Staff member to provide guidance in the removal process.

Study clinical assessments and activities are summarized in **Table 2**.

Table 2: Clinical Assessment Schedule

Required Assessments to be Collected	Baseline (Visit 1)	7 & 14-Day (Visit 2 & 3)	21-Day (Visit 4)	30-Day (Visit 5)
		±3 days Phone or Video Call only	+3 days	±3 days
Informed Consent 	X	X	-	-
Medical and Cardiac Background/History	X	-	-	-
Fitzpatrick Skin Assessment	X	-	-	-
Skin Condition Assessment  , Including photograph(s)	X	-	X	X
Assessment of Device Adhesion Performance, Including photograph(s)	-	-	X	X
Adverse Events 	X 	X	X	X

1. *Continued Informed Consent will be verified at each post-baseline contact.*
2. *Including chest hair density, as applicable.*
3. *Adverse Events include serious adverse events, all device-related complications, device deficiencies, device malfunctions, procedures and any hospitalizations. If AEs are ongoing at the 30-day visit, the participant should be contacted until resolution, or Day 37, whichever is sooner.*
4. *AEs are only assessed following Informed Consent and participant enrollment into the study.*

The study device will be returned to iRhythm Technologies, Inc. for download and analysis of the ECG signal collected during the wear.

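### Percent analyzable time is divided by wear time, which can run to day 33, while recording is programmed for at most 30 days, so for patches worn past day 30 the score depends on the removal date

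*Protocol*

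**What the plan says.** The relevant text is the same in version 01 and version 02 of the protocol, except for one visit-window label noted below.

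- **Recording limit.** Section 2.0 says the device has "programming configurations updated to allow for continuous ECG data recording for up to 30 days". In Table 1 the row "Programmed ECG Storage Duration" gives up to 30 days for the study device.
- **Measure.** Section 3.2: "Analyzable time is the percentage of time during the wear of the Zio monitor device which yields analyzable ECG signal", with analyzable glossed as free from artifact.
- **End of wear.** Under Section 3.1, wear ends when adhesion fails or when "the device is removed at the 30-day follow-up visit". There is no cap at day 30. Section 5.2 matches this: "The participant will be instructed to wear the device for as long as possible, up to the 30-day visit".
- **Date of that visit.** Section 5.6: "At day 30 following patch application and up to day 33, participants will be asked to return to the clinic". The labels disagree: the section heading says ±3 days, and Table 2 says +3 days in version 01 and ±3 days in version 02. All of them allow day 33.
- **Success rule.** Section 3.2: "The performance objective will be met if the percent analyzable time is greater than 80% in 90% of subjects".

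Section 2.0 also describes the measure in another way, as the percentage of the ECG signal that is analyzable. That could be read as using recorded time as the denominator.

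**The concern.** Wear time and recording time are different clocks, and the protocol treats them so. Section 5.2 says that if the device stops functioning, "the participant will be asked to continue wearing the non-functioning patch for as long as possible", so that wear duration is still captured. Section 3.2 puts the wear clock in the denominator, but the numerator can only fill while the device records. Once wear passes the programmed 30 days, the denominator grows and the numerator cannot.

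Percent analyzable time is one of the two pass/fail objectives, and its mean and 95% confidence interval are also reported (Section 7.4). Among participants whose patch stays on past day 30, two identical recordings could fall on opposite sides of 80% because of the appointment date alone. These are the longest wearers, whom the study hopes to produce. Each phase is judged separately (version 02, Section 7.1). With 75 analyzed, the 90% rule tolerates 7 participants at or below 80%: 68/75 = 90.7% passes and 67/75 = 89.3% does not.

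**Working it through.** **The protocol's own figure.** The only computed figure is the sample size of 61 for wear duration (Section 7.2). It reproduces: a one-sample t-test with difference 24.0 − 21 = 3 days, SD 9.3 and one-sided alpha 0.05 has power 0.801 at n = 61 and 0.795 at n = 60. This point does not affect it. No calculation is given for analyzable time.

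**Inputs.** Recording limit 30 days (Section 2.0, Table 1); denominator = days worn, W (Section 3.2); latest removal day 33 (Section 5.6); bar 80% (Section 3.2). Recording is taken to start at application.

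**Formulas.**
- Best possible score = min(W, 30) / W
- Clean share of the recording needed to reach the bar = 0.80 × W / min(W, 30)
- Artifact allowance in days = min(W, 30) − 0.80 × W

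| Removal day | Best score | Clean share needed | Artifact allowance | Score of an 85%-clean 30-day recording (25.5 days) |
|---|---|---|---|---|
| 30 | 100% | 80.0% | 6.0 days | 25.5/30 = 85.0% |
| 31 | 30/31 = 96.8% | 82.7% | 5.2 days | 25.5/31 = 82.3% |
| 32 | 30/32 = 93.8% | 85.3% | 4.4 days | 25.5/32 = 79.7% |
| 33 | 30/33 = 90.9% | 88.0% | 3.6 days | 25.5/33 = 77.3% |

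For removal or detachment on day 30 or earlier, min(W, 30) = W and nothing changes.

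**Average effect among patches still attached at the visit.** This depends on the spread of visits, which the protocol does not give. Two assumptions bracket the stated windows:
- Visits even over days 30–33: 30 × ln(33/30) / 3 = 0.953.
- Visits even over days 27–33: (3 × 1 + 30 × ln(33/30)) / 6 = 0.977.

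**Average effect over the whole study.** Let s be the share of analyzed participants still attached at the visit, also not given. If the clean share is similar in those who do and do not stay attached, the mean score is multiplied by about 1 − 0.047s (days 30–33) or 1 − 0.023s (days 27–33). At s = 0.25, 0.50 and 0.75 the first gives 0.988, 0.977 and 0.965; the second gives 0.994, 0.988 and 0.982.

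**The case against.** The best counter-argument is that Section 2.0 calls the measure a percentage of ECG signal. If signal is the denominator, unrecorded days drop out and a flawless recording scores 100% whatever the removal date. The derivation could also be spelled out in a statistical analysis plan that is not shown. What stands is that the protocol has two descriptions. But Section 3.2 is the section that defines the objective, and it says time during wear. Since the protocol itself fixes the denominator, and does so at odds with the recording limit, this is not merely a detail left for later.

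Other limits also stand:

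- The ±3-day labels may allow visits before day 30, which halves the average effect in the calculation above.
- With a planning mean of 24.0 days and SD 9.3, many patches may come off before day 30 and be untouched.
- The 88.0% requirement applies at day 33 only. A recording that is 97% clean still scores 0.97 × 30/33 = 88.2% there and passes.
- Nothing in the protocol shows that any participant will fall in the affected band.

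A reader might infer that Signal Artifact in Section 3.4 has the same defect. It does not: that measure is a proportion of ECG signal, and days without recording contribute none. A reader might also suppose that the device records beyond 30 days. The protocol does not say so; if it does, the 30-day statements need correcting instead.

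**Conclusion.** The point holds in a limited form. Read literally, Section 3.2 lets up to 3 unrecordable days into the denominator of a pass/fail measure. For patches worn past day 30 only, the effective requirement on the recording rises from 80% to between 82.7% and 88.0% for removal on days 31 to 33. A participant's result can then turn on the appointment date.

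A reader might go further and conclude that the 80% bar cannot be reached, that every score shrinks by about 5%, or that the study could pass wrongly. The documents support none of these. A flawless recording scores at least 90.9%. The 0.953 multiplier assumes visits spread evenly over days 30–33 and applies only to patches still attached at the visit. The bias can only count against the device. Whether it would change the study's verdict cannot be told, because neither the share worn past day 30 nor the distribution of signal quality is given. The conclusion rests on the wear-time wording of Section 3.2 and on recording stopping at the programmed 30 days.

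**What to change.** In Section 3.2, define percent analyzable time as analyzable ECG time divided by the shorter of wear time and the programmed 30 days (720 hours). Align the Section 2.0 description with it. A plain recorded-time denominator would also remove the dependence on visit date, but it would hide device failure before day 30; the capped version keeps that failure in the score. Section 3.4 needs no change, and the fix does not depend on the visit window.

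The cost is one clause in Section 3.2 and one aligned sentence in Section 2.0, with no new data. Analyzable time comes from the device download. The end of wear comes from the removal and detachment times that the study already records, so the download alone is not enough.

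Version 02 states that Phase 1 enrollment was complete by 28 February 2025, so Phase 1 wear would have ended by about 2 April 2025 (33 days later), before version 02 was released on 23 April 2025. For that phase, the report should say which denominator was used and show the result under both.
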